3.3 Study Subjects

3.3.1 Subject Disposition and Completion Status

The number of subjects enrolled in the CD1145 study will be summarized overall and by site number. In addition, disposition of subjects throughout the CD1145 study with respect to completion of treatment will be provided overall and overtime (year 1, year 2, year 3). Disposition of subjects with respect to completion of study will also be provided.

3.3.2 Demographics and Baseline Characteristics

Demographics including age in years at Day 1 of CD1145 study, gender, ethnicity, race, weight, height, and body mass index (BMI) will be summarized. A summary of baseline disease characteristics may include, but not be limited to baseline Systemic Lupus Erythematosus Disease Activity Index - 2000 (SLEDAI-2K) score, Systemic Lupus International Collaborating Clinics/American College of Rheumatology Index (SLICC/ACR) damage index score, baseline corticosteroids and other immunosuppressives use, anti-dsDNA

(positive, negative), C3 (normal, abnormal), C4 (normal, abnormal), antinuclear antibody (ANA) status (positive, negative), and 4-gene type I IFN diagnostic (high, low).

3.3.3 Study Drug Exposure

The number of doses received (300 mg, 1000 mg, and total) and the amount of study drug given in mg will be summarized. For a particular subject, the total anifrolumab exposure will be defined as the sum of study drug (mg) received from all administrations.

3.3.4 Concomitant Medications

Concomitant medications will be coded using World Health Organization Drug Dictionary (WHO-DD). Non-immunomodulatory medications and immunomodulatory medications used during the study will be summarized by the Anatomical Therapeutic Chemical (ATC) Class level 1 and Preferred Term.

3.4 Exploratory Efficacy Endpoints and Analyses

3.4.4 Handling of Dropouts and Missing Data

If one or some components of SLEDAI-2K are missing, then the last observation carried forward (LOCF) approach will be used to impute the missing component score. No imputation will be performed for missing data in other variables.

3.5 Patient Reported Outcomes

3.5.1 Short Form-36 Version 2 (SF-36v2)

Impact on HRQL will be assessed using the SF-36v2. The SF-36v2 consists of 36 items. These 36 items yield 8 domains of functional health and well-being. These domains include Physical Functioning, Role Physical, Bodily Pain, General Health, Vitality, Social Functioning, Role Emotional, and Mental Health. The 8 domains can further be combined to provide 2 summary measures: 1) Physical Component Summary (PCS); and 2) Mental Component Summary (MCS). The range of SF-36v2 score and scales is 0-100, with a higher score indicating better HRQL.

The PCS, MCS, and domain scores of 8 domains as well as their change from baseline will be summarized by visit.

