Subjects who are permanently discontinued from receiving investigational product will be followed for safety per Section 6.4, including the collection of any protocol-specified blood or urine specimens, unless consent is withdrawn or the subject is lost to follow-up or enrolled in another clinical study. Twenty-eight days (\pm 7 days) after the last dose of investigational product, subjects will begin the follow-up period by completing the Visit 41/Early Discontinuation Visit assessments. Two subsequent follow-up visits will also be completed 59 and 85 days (\pm 7 days) after the last dose of investigational product as per the schedule of study procedures. A subject who receives any SLE medication or SLE treatment listed in Appendix 3 (other than those prohibited medications or treatments listed above) may be allowed to continue receiving investigational product only if permission from the sponsor is obtained.

Concomitant medications that require the sponsor to be notified immediately and the medical monitor to be consulted to determine if a subject may continue to receive investigational product include, but are not limited to:

- Corticosteroids with a long biologic half-life (eg, dexamethasone, betamethasone)
- Increase in oral corticosteroids (OCS) treatment above a total dose > 40 mg/day for a dosing period > 14 days, dosing with MEDI-546 may be continued, unless there is a safety concern. However, it should be noted that frequent steroid use above Study CD-IA-MEDI-546-1013 baseline for SLE disease control (> 2 times every 6 months, higher doses [> 40 mg/day], and/or longer duration than permitted by the protocol) after 12 months of open-label MEDI-546 should result in discontinuation of MEDI-546 administration for failure to achieve a favorable benefit:risk profile.

Withdrawal of consent: If consent is withdrawn, the subject will not receive any further investigational product or further study observation. Note that the subject may need to undergo additional tests or tapering of treatment to withdraw safely.

Lost to follow-up: Subjects will be considered lost to follow-up only if no contact has been established by the time the study is completed (as defined in Section 4.9) such that there is insufficient information to determine the subjects' status as of their last visit.

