4.5.2.1 Corticosteroids

When OCS treatment is above a total dose > 40 mg/day for a dosing period > 14 days, dosing with MEDI546 may be continued, unless there is a safety concern.

However, it should be noted that frequent steroid use above Study CD-IA-MEDI-546-1013 baseline for SLE disease control (> 2 times every 6 months, higher doses [> 40 mg/day], and/or longer duration than permitted by the protocol) after 12 months of open-label MEDI-546 should result in discontinuation of MEDI-546 administration for failure to achieve a favorable benefit:risk profile.

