5.1.3 Follow-up Period

5.1.3.1 28 Days after the Last Dose (+/- 7 Days): First Safety Follow-up Visit or Early Discontinuation Visit (Visit 41)

- 1. Record concomitant medications
- 2. Take vital signs
- 3. Collect blood samples for:

- Serum chemistry
- Hematology
- SLEDAI-2K-associated lab tests (C3, C4, CH50 complement, anti-dsDNA)
- Immunology profile (ANA, extractable nuclear antigens [RNP, Sm, SSA, SSB], quantitative immunoglobulins)
- Pharmacokinetics (MEDI-546 serum concentration)
- Pharmacodynamics (type I IFN signature with 21-gene assay)
- Immunogenicity (ADA to MEDI-546)
- Proteomics/biomarkers (optional)
- 4. Collect urine sample for:
 - Urinalysis
 - Urine β-HCG (dipstick; females of childbearing potential only, ensure result is negative)
 - SLEDAI-2K-associated lab tests: urine protein/creatinine ratio
 - Urine biomarker (optional)
- 5. Perform SLEDAI-2K
- 6. Assess worsening and/or flare of SLE disease activity using SLE Increase in Disease Activity CRF and complete for SLE related AEs that are not serious, if applicable.
- 7. Evaluate subject for signs and symptoms of TB using a TB surveillance form
- 8. Assess for AEs/SAEs/AESIs (nonserious AEs will only be captured during the first year of subject's participation in the study; however, nonserious AEs that result in interruption of investigational product and/or discontinuation from the study will be captured at any time during the subject's participation in the study)

5.1.3.2 59 Days after the Last Dose (+/- 7 Days): Second Safety Follow-up Visit (Visit 42)

- 1. Record concomitant medications
- 2. Take vital signs
- 3. Collect urine sample for:
 - Urine β -HCG (dipstick, females of childbearing potential only, ensure result is negative)
- 4. Assess worsening and/or flare of SLE disease activity using SLE Increase in Disease Activity CRF and complete for SLE related AEs that are not serious, if applicable
- 5. Evaluate subject for signs and symptoms of TB using a TB surveillance form
- 6. Assess for AEs/SAEs/AESIs (nonserious AEs will only be captured during the first year of subject's participation in the study; however, nonserious AEs that result in interruption

of investigational product and/or discontinuation from the study will be captured at any time during the subject's participation in the study)

5.1.3.3 85 Days after the Last Dose (+/- 7 Days): Third Safety Follow-up Visit (Visit 43)

- 1. Administer SF-36v2 (should be completed prior to any clinical assessments)

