2.4 Sample Size

Sample size estimation is based on the number of subjects who have completed the treatment period of study CD1013. A total of 307 subjects have been randomized in study CD1013. Assuming that 20% of subjects will be lost to follow up or discontinue from study CD1013, there will be a total of approximately 240 subjects who will be eligible for this long-term safety study.

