3.2 Analysis Populations

3.2.1 Definition of Analysis Populations

The analysis populations are defined in Table 3.2-1.

Table 3.2-1 Analysis Populations

Population	Description
As-treated population	Subjects who receive any study investigational product in the OLE study will be included in the as-treated population.

All analyses will be performed on the As-treated population unless otherwise specified.

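### By-visit SF-36v2 change on observed cases can be biased upward from Week 72 to Week 156, because poorly controlled subjects should stop drug after month 12 and no SF-36v2 is taken at the Early Discontinuation Visit

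*SAP*

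**What the plan says.** **Analysis.** SAP 3.5.1 names the SF-36v2 as the measure of impact on health-related quality of life (HRQL). Its whole method is: "The PCS, MCS, and domain scores of 8 domains as well as their change from baseline will be summarized by visit". SAP 3.4.4 carries forward missing SLEDAI-2K components and then states: "No imputation will be performed for missing data in other variables". SAP 3.2.1 defines the population broadly ("Subjects who receive any study investigational product in the OLE study will be included in the as-treated population"), but without imputation or a model the n behind each visit mean falls as subjects leave. SAP 3.3.1 reports treatment completion by year and does not link it to SF-36v2.

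**Exit rule.** Protocol 4.2.3 says that frequent steroid use for SLE control above the parent-study baseline "after 12 months of open-label MEDI-546 should result in discontinuation of MEDI-546 administration for failure to achieve a favorable benefit:risk profile". Sections 4.5.2, 4.5.2.1 and 4.6.1 carry the same rule. Section 3.1 also asks the investigator to weigh risk and benefit at every visit.

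**Collection.** On treatment, SF-36v2 is taken at Day 1, at Weeks 24, 48, 72, 96, 120 and 144, and at Week 156 (Protocol 5.1.2.1, 5.1.2.4, 5.1.2.6). For subjects taken off drug, Protocol 4.2.3 says that 28 days after the last dose "subjects will begin the follow-up period by completing the Visit 41/Early Discontinuation Visit assessments". Section 5.1.3.1 and Table 5.1-2 list no SF-36v2 at that visit. The one follow-up SF-36v2 is at Visit 43, 85 days after the last dose.

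**Windowing.** SAP 3.1.1 maps assessments to scheduled visits by bisected windows and leaves the detail to the statistical programming plan, which is not among the documents. The SAP does not say whether an early leaver's Visit 43 score counts as follow-up or enters a scheduled week.

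**The concern.** Because the exit rule acts on disease control, those who stay after month 12 may be a favourable selection. The late visit means describe subjects still on drug and can be read as describing everyone treated. A sustained or slowly rising mean in years 2 and 3 could then be taken as durable benefit when part of it is selection. A single-arm open-label study has no control group to reveal this.

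The schedule widens the gap. The last on-drug score may be up to 24 weeks before the stop, and the only later score is off drug. No planned display sets the scores of early leavers beside those of subjects who completed treatment.

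**Working it through.** **1. The plan's own figure.** SAP 2.4 gives 307 randomised in the parent study and states: "Assuming that 20% of subjects will be lost to follow up or discontinue from study CD1013". 307 × 0.80 = 245.6, which agrees with its approximately 240. This 20% is a loss before the extension. The documents give no extension dropout rate.

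**2. Illustrative retention.** Suppose a fraction L is lost per 422 days (the parent-study length) at a constant rate. Retention at Week 156 (1092 days) is (1 − L)^(1092/422).

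| L (assumed) | Retained | Missing of 240 |
|---|---|---|
| 10% | 0.761 | 57 |
| 20% | 0.561 | 105 |
| 30% | 0.397 | 145 |

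**3. Simulated observed-case bias.** Assumptions, none from the documents: true mean change +4 at every visit, SD of change 8, within-subject correlation 0.6, and 400,000 subjects at the seven on-treatment visits from Week 24 to Week 156. For visits after Week 48, the dropout hazard is multiplied by exp(−s × z), where z is the previous standardised score, and rescaled to the same overall loss. For s = 0.25, 0.5 and 0.7 the hazard ratio per SD worse is 1.28, 1.65 and 2.0. Visit 43 scores are left out.

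- L = 20%: inflation at Week 156 is 0.53, 0.97 and 1.32 points.
- L = 10%: 6% to 16% of the true change, or 0.24 to 0.64 points (4 × 0.06; 4 × 0.16).
- L = 30%: 20% to 52%, or 0.80 to 2.08 points (4 × 0.20; 4 × 0.52).
- s = 0: no bias at any loss.

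**4. Cross-check by formula.** With true change 0, the observed-case mean is ρ × SD × φ(z_d)/(1 − d). Here d is the share gone, z_d is the normal quantile of d, and ρ is the correlation between tendency to leave and SF-36v2 change. SD = 10 is the general scaling in Protocol 5.2.15.1, not an SD of change. For d = 0.20 and ρ = 0.4: 0.4 × 10 × 0.280/0.80 = 1.40. Over ρ = 0.2 to 0.6 the result is 0.4 to 1.2 points at d = 10%, 0.7 to 2.1 at 20% and 1.0 to 3.0 at 30%. It is 0 at ρ = 0.

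**5. Effect of Visit 43.** With bisected windows on the SF-36v2 schedule and nominal dates, Visit 43 after a last dose at Weeks 48 to 68 maps to Week 72, after Weeks 72 to 92 to Week 96, after Weeks 96 to 116 to Week 120, after Weeks 120 to 136 to Week 144, and after Weeks 140 to 152 to Week 156. Each leaver adds at most one off-drug value. In a simulation with true change 0, SD 10, 20% gone, ρ = 0.4 and exits spread over Weeks 52 to 156:

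| Week | Bias without Visit 43 | Bias with Visit 43 windowed in |
|---|---|---|
| 72 | 0.23 | 0.00 |
| 96 | 0.53 | 0.23 |
| 120 | 0.84 | 0.51 |
| 144 | 1.22 | 0.85 |
| 156 | 1.39 | 1.20 |

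**6. How far a model helps.** In the step 3 setup, a likelihood-based repeated-measures estimate has bias of at most about 0.03 points. That follows from how dropout was generated: it depended on an observed score, so data are missing at random (MAR). When dropout depends on the current, unrecorded score, the likelihood estimate keeps roughly 0.1 to 0.35 points of bias at 20% loss and about 0.6 at 30%.

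**The case against.** SF-36v2 is neither the primary nor the secondary endpoint. The SAP promises no test and no durability claim, and it already shows attrition by year. The exit rule is triggered by steroid use, not by a quality-of-life score. Other reasons for stopping, such as adverse events, pregnancy or withdrawn consent, need not raise the mean. Subjects taken off drug still attend Visit 43 unless they withdraw consent, are lost or enter another study. A model on on-treatment values answers a different question: what change would be expected had everyone stayed on drug.

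All of this stands, and it limits the point. A reader might infer that the late means will drift upward with no real improvement. The documents do not support that, because they contain no link between exit and SF-36v2. A reader might also take 105 missing subjects as a forecast, but it only carries a parent-study assumption forward to people who largely completed that study. Nor does a repeated-measures model remove the bias in general, as step 6 shows.

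The objection does not remove the gap itself. Part of the discontinuation is tied to disease control by rule, the score nearest the stop is not collected, and no planned SF-36v2 table would show whether leavers differ.

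**Conclusion.** The Week 72 to Week 156 SF-36v2 means can be biased upward if leavers have worse HRQL, and the SAP has no display that would reveal it. Under the step 3 assumptions the Week 156 inflation is about 0.2 to 2.1 points on a true change of 4. It is zero if exit is unrelated to SF-36v2, and somewhat smaller if Visit 43 scores are windowed in. The true size cannot be derived from the documents. Only the interpretation of a descriptive outcome is affected, so this is a minor recommendation.

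**What to change.** In SAP 3.5.1:

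- Keep the observed-case table and print n at each visit.
- Add, as supplementary, change from baseline at the last on-treatment SF-36v2 for all treated subjects, split by completed treatment versus stopped early.
- Add, as supplementary, a repeated-measures model for PCS and MCS on on-treatment values. Label it as the change expected had subjects stayed on drug, under MAR. Include one missing-not-at-random sensitivity analysis, for example a delta adjustment. It belongs beside the observed-case table and should not replace it.
- State that Visit 43 scores of early leavers are shown as off-drug follow-up and are not windowed into scheduled on-treatment weeks. Windowing them in would lower the bias somewhat but would mix off-drug with on-drug scores.

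In Protocol 5.1.3.1 and Table 5.1-2, add the SF-36v2 at Visit 41/Early Discontinuation Visit for subjects who stop before Week 156.

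The cost is a few extra tables from data already collected and one self-completed questionnaire at an existing visit. The model still relies on MAR, and the late figures may look slightly less favourable.

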3.6 Pharmacodynamic Endpoint and Analyses

3.6.1 Type I IFN Signature

The 21-gene type I IFN signature in whole blood will be used as a PD marker. The gene signature and the neutralization levels will be summarized by visit. Subgroup analysis of 21-gene type I IFN signature will be performed based on ADA status (positive vs negative).

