1 INTRODUCTION

1.1 Disease Background

Systemic Lupus Erythematosus

The disease pathogenesis of systemic lupus erythematosus (SLE) includes activation of innate immunity, with increased production of type I interferons (IFNs), including interferon-alpha (IFN- α), and increased numbers of plasmacytoid dendritic cells (pDCs) and myeloid dendritic cells (mDCs) in involved tissue (Bengtsson et al, 2000; Baechler et al, 2003; Crow and Wohlgemuth, 2003; Ronnblom and Alm, 2003; Baechler et al, 2004; Banchereau et al, 2004; Dall'era et al, 2005; Crow, 2010). Specific parts of the humoral and cellular immune systems are activated. Autoantibodies are present universally and may precede development of clinically apparent disease (Arbuckle et al, 2003). Systemic lupus erythematosus-associated autoantibodies include anti-double-stranded (ds) deoxyribonucleic acid (DNA), anti-nucleosomes, anti-ribonucleoprotein (RNP) complex, and anti-Smith (Sm) antibodies (Rahman and Isenberg, 2008). Immune complexes containing anti-dsDNA or anti-RNP antibodies can activate type I IFN production (Bengtsson et al, 2000; Ronnblom and Alm, 2003).

Multiple lines of evidence indicate a role of type I IFNs in the pathogenesis of SLE:

- Genetic polymorphisms associated with type I IFNs are associated with susceptibility to SLE (Criswell, 2008; Sigurdsson et al, March 2008; Sigurdsson et al, September 2008).
- High IFN-α levels and type I IFN activity have been reported in SLE (Bengtsson et al, 2000; Dall'era et al, 2005).
- Increased levels of messenger ribonucleic acid (mRNAs) whose transcriptions are induced by type I IFNs (type I IFN signature) are prominent in peripheral blood mononuclear cells (PBMCs) and whole blood in approximately 60% of SLE patients and are associated with greater disease activity (Baechler et al, 2003; Bennet et al, 2003; Crow and Wohlgemuth, 2003; Kirou et al, 2004; Kirou et al, 2005; Feng et al, 2006). Transcripts induced by type I IFN are the most overexpressed transcripts in SLE (Yao et al, 2010).
- Proteins induced by IFN are increased in SLE patients (Hylton et al, 1986; Okamoto et al, 2004; Huang et al, 2008).

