7.2 Analysis Populations

The Safety Population includes all subjects who receive any amount of investigational product. Demographics, safety endpoints, IM, PD, and disease activity will be summarized based on the Safety Population. Additional analysis populations may be defined as needed.

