3.2.2 Treatment Groups for Analysis

Treatment group is Anifrolumab Total for all analyses except the exposure adjusted adverse event which will be summarized by Anifrolumab 300 mg, Anifrolumab 1000mg, and Anifrolumab Total.

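### SAP 3.6.1 pools type I IFN neutralization over all treated subjects regardless of baseline IFN status, which probably dilutes and blurs the descriptive PD summary

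*SAP*

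**What the plan says.** SAP 3.6.1 uses the 21-gene signature in whole blood as the PD marker and states: "The gene signature and the neutralization levels will be summarized by visit". Its only subgroup sentence is: "Subgroup analysis of 21-gene type I IFN signature will be performed based on ADA status (positive vs negative".

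No population is named there, so SAP 3.2.1 governs: "All analyses will be performed on the As-treated population unless otherwise specified". Protocol 7.2 agrees: "Demographics, safety endpoints, IM, PD, and disease activity will be summarized based on the Safety Population". SAP 3.2.2 puts both dose levels in one column: "Treatment group is Anifrolumab Total for all analyses except the exposure adjusted adverse event".

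On IFN status, Protocol 1.1 reports the signature in "whole blood in approximately 60% of SLE patients and are associated with greater disease activity". The OLE entry criteria in Protocol 4.2.1 and 4.2.2 do not select on it. SAP 3.3.2 lists the 4-gene diagnostic, high or low, among the baseline characteristics. SAP 3.8.7 splits AEs and SAEs by it. SAP 3.7.1 limits the by-visit ANA and ENA results to subjects who were abnormal at baseline.

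SAP 3.1 defines baseline as the last value up to OLE Day 1 before dosing. Protocol 5.1.2.1 schedules both the 4-gene and the 21-gene sample predose on that day.

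**The concern.** Neutralization describes the lowering of a raised signature. A subject with no raised signature has little to lower, and a ratio to a normal baseline is then mostly measurement noise. Averaging such subjects with those who have a signature mixes two different quantities. The SAP already applies the opposite logic to ANA and ENA, and it already holds the variable needed to do the same here.

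What is at stake is how readable the PD result is. A pooled mean could make the drug's PD effect look weaker and more variable than it is in the subjects where it can be measured. There is a second, smaller issue. Protocol 7.3.2 asks for the association of ADA titers with PD markers, and SAP 3.9 gives only ADA counts and titers. The ADA split in SAP 3.6.1 is therefore the only visible ADA-PD comparison. It takes no account of IFN status, which affects both where the signature starts and how far it can fall.

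**Working it through.** **The plan's own figure.** SAP 2.4 starts from 307 randomized subjects and assumes 20% loss: 307 x 0.80 = 245.6, consistent with its approximately 240. The documents give no effect size, SD or formula for the PD endpoint, so no PD figure can be reproduced. What follows rests on assumptions.

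**Assumptions.**
- Neutralization = 100 x (1 - visit value / baseline value).
- Share of IFN-high subjects p = 0.60, the background figure in Protocol 1.1. Ranges are shown.
- Mean neutralization in IFN-high subjects E = 80% or 90%, with SD 8 points.

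**1. Dilution with zero neutralization in IFN-low subjects.** Pooled mean = p x E.
- 0.60 x 80 = 48% and 0.60 x 90 = 54%.
- At E = 80%, p = 0.5 gives 40% and p = 0.8 gives 64%.
- Mixing the two groups alone adds a between-group SD of E x sqrt(p(1 - p)) = 80 x sqrt(0.24) = 39 points.

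**2. Dilution with noise in IFN-low subjects.** Let independent log-scale noise of SD s act at baseline and at the visit. The expected ratio is exp(s²), and its SD is exp(s²) x sqrt(exp(2s²) - 1).

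| s | Mean neutralization | SD |
|---|---|---|
| 0.2 | 100 x (1 - 1.041) = -4% | 30 points |
| 0.4 | 100 x (1 - 1.174) = -17% | 72 points |

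Pooled mean, lowest: 0.60 x 80 + 0.40 x (-17) = 41%. Highest: 0.60 x 90 + 0.40 x (-4) = 52%. Steps 1 and 2 together give 41-54%.

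**3. The median.** If nearly all IFN-low values lie below the IFN-high values, the pooled median sits at quantile (0.50 - 0.40) / 0.60 = 1/6 of the IFN-high distribution, which is z = -0.97. The fall is 0.97 x 8 = about 8 points, giving 72% or 82%. This protection depends on p. At p = 0.5 the quantile is (0.50 - 0.50) / 0.50 = 0, so the median drops to the gap between the groups.

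**4. Noise as a function of baseline level.** A separate simulation assumed log2 error SD of 0.3-0.5 and 80% suppression of the excess over normal. The SD of percent neutralization was 31-59 points at a true baseline fold change of 1.0, against 9-17 points at a fold change of 10. Without noise this model gives 80 x (b - 1) / b at baseline fold change b: 0% at 1, 40% at 2, 64% at 5 and 72% at 10. The same drug action therefore reads differently according to baseline level.

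**5. ADA groups.** With p = 0.60 in both groups, the expected difference in IFN-high share is zero. By chance alone its SD is sqrt(0.24 x (1/n + 1/(240 - n))), where n is the number of ADA-positive subjects. Assumed ADA rates of 5, 10 and 20% give n = 12, 24 and 48, and SDs of 14.5, 10.5 and 7.9 percentage points of share. The documents give neither an ADA rate nor a relation between ADA and IFN status.

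**6. After the change.** The IFN-high summary estimates E itself. At p = 0.60 it keeps 240 x 0.60 = 144 subjects; for p = 0.5 to 0.8 it keeps 120 to 192.

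**The case against.** The strongest reply is that the definition may exist out of sight. In the public copy, Protocol 5.2.11 on the 21-gene assay is a bare heading, the exploratory objectives and endpoints are missing or redacted, and the visible part of SAP 3.4 starts at 3.4.4. SAP 1 also refers to a separate programming plan with table templates and specifications. A formula or a restriction to signature-positive subjects could sit in any of these. This stands, and it is why the figures here are conditional.

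It is also fair that the SAP reports medians as well as means, and the median suffers much less at 60% IFN-high. The 60% is a literature figure. Protocol 1.1 links the signature to greater disease activity, and this population has moderately to severely active disease, so the share here may differ.

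A reader might infer that the ADA comparison is confounded, or that ADA groups will show a false gap in neutralization. The documents do not support that. The ADA sentence names the 21-gene signature, not neutralization, and nothing shows that IFN status differs between ADA-positive and ADA-negative subjects. The supportable statement is that the comparison is unadjusted.

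A reader might also conclude that IFN-low subjects should be dropped. That goes too far, because showing both groups loses nothing.

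**Conclusion.** The point holds as a low-severity improvement. On the visible text, neutralization is summarized over all treated subjects without regard to baseline IFN status, although the SAP has that status and uses it elsewhere. If neutralization is a percent reduction from baseline and 60% of subjects are IFN-high, a true mean of 80-90% would appear as about 41-54%, with the median down by about 8 points. The size moves with the formula, the IFN-high share and the assay noise, none of which the documents give for this trial. The ADA split of the signature is open to chance imbalance or confounding by IFN status, but neither is demonstrated.

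It would be wrong to read this as a threat to the study's main conclusions. The PD analysis is descriptive, the primary endpoint is treatment-emergent AEs and SAEs with no formal testing (Protocol 7.3.1), and neither the sample size nor any error rate depends on it.

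**What to change.** In SAP 3.6.1:

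- Define neutralization by its formula and its reference value.
- Present it by 4-gene high/low status, as SAP 3.8.7 does for AEs. Make IFN-high the main PD summary, and show IFN-low subjects as signature level by visit.
- Take the IFN classification and the neutralization denominator from the same stated sample, either OLE Day 1 or a parent-study pre-drug baseline. Protocol 1.2.3 describes 1:1:1 randomization with two active arms, so about two thirds of randomized subjects had prior anifrolumab. Classifying on a pre-drug sample while dividing by an OLE Day 1 value would leave an unstable denominator in anyone still suppressed on that day.
- Present the ADA split of the 21-gene signature within IFN-high subjects.

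The cost is a few sentences and one extra table split. The main neutralization table becomes smaller: about 144 of 240 subjects if 60% are IFN-high. Using OLE Day 1 needs no new data, since both assays are scheduled then. Using a parent-study baseline means bringing in parent-study data, and the documents do not show which assays were done there.
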